The risk is also greater with smoking, obesity, premature postsurgery exercise, heavy lifting, recurrent vomiting, coughing, or an improper diet that leads to constipation.

Any wound dehiscence needs to be treated as a new wound and is a surgical emergency that requires immediate attention. Surgical debridements, antibiotic therapy, reclosure with the appropriate surgical technique, and sutures represent the most appropriate treatments. Finally, the patient's wound should be closely monitored to prevent dehiscence from recurring.

For all the above mentioned reasons, wound dehiscence always needs to be prevented as much as possible.

Therefore, a new, polyurethane-based topical skin adhesive has been developed: MAR-CUTIS. MAR-CUTIS is intended for topical application to close wounds of the skin, such as cuts and wounds from surgical incisions. It consists of a polyurethane-based prepolymer and an amino acid-based hardening agent which are provided in prefilled, double syringes with a mixing cannula and spreader tip.

Information about the preclinical testing as well as known and expected benefits, risks, serious adverse events (SAEs) and reasonably anticipated adverse events (AEs) of MAR-CUTIS are to be found in the Investigator's Brochure.

In particular, there are some predictable AEs (rates) that have been observed with other skin adhesives and can be possibly associated with the use of MAR-CUTIS:

- Infection (3.6%) after wound closure; this also applies to sutures and is not limited to adhesives.
- Dehiscence (2.5%) which is greater in wounds closed with skin adhesive as compared to other methods of wound closure (namely sutures, staples and strips).
- Improper application of the skin adhesive (unknown).

- Allergic reactions (11.5%).
- Other additional risks mentioned in risk management file, eg, pain (6.1%), edema (9.7%), and warmth (1.3%).

Such novel polyurethane-based medical adhesive differs from existing technologies due to its unique composition. The adhesive technology is:

- Fully Synthetic
- Easy to use
- Flexible

Based on polyurethane, it is completely different from existing skin adhesives based on cyanoacrylate. This new component is adhering to the tissue via mechanical and physical adhesion, forming a strong, yet flexible film. There is no reaction with the tissue itself; a strong polymer network is quickly formed and full polymerization is completed after a few minutes.

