
 
To compare the wound infection incidence between both treatment groups.
 
	
 
Wound infection incidence assessed at the Day 10, Month 1, and Month 3 visits or at the Early Discontinuation visit (diagnosed according to the Centers for Disease Control and Prevention [CDC] criteria for surgical site infection [Section 15.1]).
 
Wound infection assessed on a binary scale (“1 - yes” or “0 - no”) for the following criteria: 
 
Presence of erythema
 
Presence of edema
 
Presence of pain at rest
 
Presence of elevated temperature
 
 A total score will be calculated for each subject.
 

 
To evaluate the investigator satisfaction with the cosmetic outcome after the closure of the target surgical incision/laceration with MAR-CUTIS versus Dermabond Advanced.
 
	
 
Investigator-completed POSAS done at the Month 1 and Month 3 visits or at the Early Discontinuation visit (if Early Discontinuation occurs before Month 1).
 

	

Investigator-completed Modified Hollander Cosmesis Scale (mHCS) done at the Day 10 and Month 1 visits or at the Early Discontinuation visit (if Early Discontinuation occurs before Month 1).

To evaluate the subject comfort with the device during and after treatment with MAR-CUTIS versus Dermabond Advanced.

	

A questionnaire related to subject experience and satisfaction with the device completed by the subject at the Day 10 and Month 1 visits or at the Early Discontinuation visit (if Early Discontinuation occurs before Month 1).

A subject-related questionnaire completed by the investigator at the Day 0 and Month 1 visits or at the Early Discontinuation visit (if Early Discontinuation occurs before Month 1).

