### 7.1.2 Schedule of Assessments

	D -21 to 0	D0	D1	D10	Month 1	Month 3	ED
Visit Window			12 hours up to 36 hours after application	±2 days	±7 days	±14 days	
Obtain written informed consent/assent	X						
Check inclusion/exclusion criteria	X	X					
Record demographic data and medical/surgical history a	X						
Perform a urine $\beta$ -hCG pregnancy test (if applicable)		X					
Allocate subject to treatment and issue a diary		X					
Application of device		X					
Document prior (within the last 2 weeks) and concomitant medication intake (including steroids, immunosuppressants, chemotherapy, anticoagulants, antibiotics. Excluding related to intraoperative anesthesia)	X	X	X	X	X	X	X
Record of adverse events	X	X	X	X	X	X	X
Record of incidents and device performance, device-related complaints		X	X	X	X	X	X
Evaluation of incision/laceration (incidence and grading)		X					
Evaluation of dehiscence			X	X	X		X d
Evaluation of wound infection				X	X	X	X
mHCS completed by investigator				X	X		X d
POSAS completed by subject and investigator					X	X	X d
Subject-completed satisfaction questionnaire				X	X		X d
Subject-related questionnaire completed by investigator c		X			X		X d
Product-related questionnaire completed by investigator					X b		X d
Subject diary collection					X		X d

Abbreviations:  $\beta$ -hCG=beta human chorionic gonadotropin; D=Day; ED=early discontinuation; mHCS= Modified Hollander Cosmesis Scale; POSAS= Patient and Observer Scar Assessment Scale.

---

a In particular, the following information will be collected: body mass index, medical history (including diabetes mellitus, chronic obstructive pulmonary disorder, hematological and vascular disorders, disorders of immune system, congestive heart failure, cardiovascular disease), concomitant medications (excluding related to intraoperative anesthesia), smoking, alcohol abuse.

b The product-related questionnaire is completed by the investigator only once per site when the last subject randomized at the site completes the Month 1 visit.

c Also completed if there is premature removal of the adhesive.

d Only to be performed if Early Discontinuation is before the Month 1 Visit or if the questionnaire has not previously been completed/if the diary has not previously been collected.

---

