## 8.2 Follow-up Period

Subjects treated for lacerations may not be able to attend the Day 1 visit since they are usually not hospitalized. In this case, all attempts should be made to obtain information on potential dehiscence and AEs by phone. The reason for non-attendance should also be reported.

In case a subject is not able to attend the Day 10 visit, a telephone call can be done to capture the primary endpoint variables information. However, this is only allowed for exceptional cases and the reason for non-attendance and potential dehiscence and AEs should be recorded.

### 8.2.1 Day 1

The following procedures will be performed at Day 1:

- Record concomitant medication.
- Record AEs.
- Record of incidents and device performance, device-related complaints.
- Evaluation of dehiscence (incidence and grading).

### 8.2.2 Day 10 and Month 1

The product-related questionnaire will be completed by the investigator only once per site when the last subject randomized at the site completes the Month 1 visit.

The following procedures will be performed at both Day 10 and Month 1:

- Record concomitant medication
- Record AEs
- Record of incidents and device performance, device-related complaints

- 
- Evaluation of dehiscence (incidence and grading)
  - Evaluation of wound infection, if an infection occurred (incidence and criteria score)
  - Modified Hollander Cosmesis Scale (mHCS) completed by investigator
  - Subject-completed satisfaction questionnaire

Additional procedures performed at Month 1 include:

- Patient and Observer Scar Assessment Scale (POSAS), completed by subject and investigator
- Subject-related questionnaire completed by investigator
- Collect subject diary

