### 9.3.6 Other Safety Assessments

Wound infection incidence, diagnosed according to the CDC criteria for surgical site infection, will be assessed by an investigator at the Day 10, Month 1, Month 3/Early Discontinuation, and any unscheduled study visits. In addition, the infection will be assessed on a binary scale (“1 - yes” or “0 - no”) for the criteria below. A total score will be generated for each subject.

- Presence of erythema
- Presence of edema
- Presence of pain at rest
- Presence of elevated temperature

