13.2.3.2 Wound infection evaluated with a binary scale

Wound infection will be additionally assessed at the same timepoints by calculating a Wound Infection Score utilizing a binary scale as follows:

$$\text{Wound Infection Score} = I_{\text{erythema}} + I_{\text{edema}} + I_{\text{pain_rest}} + I_{\text{elevated_temperature}},$$

where the four indicator variables above are equal to 1 if the wound reported the presence of erythema, edema, pain at rest or elevated temperature, and equal to 0 if the presence of each category is not recorded or is missing. Thus, the Wound Infection Score will have a maximum value of 4, and a minimum value of 0.

Descriptive statistics of the Wound Infection Score will be presented by visit.

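### Protocol Section 8 collects the four local wound signs only once an infection is found, although other sections promise a sign score for every subject and the SAP codes unrecorded signs as absent

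*Protocol*

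**What the plan says.** **Visit procedures.** Protocol 8.2.2 (Day 10 and Month 1), 8.2.3 (Month 3) and 8.2.4 (Early Discontinuation) carry the same line: "Evaluation of wound infection, if an infection occurred (incidence and criteria score". The criteria score is the count of erythema, edema, pain at rest and elevated temperature.

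**Schedule.** The row "Evaluation of wound infection" in 7.1.2 is marked at Day 10, Month 1, Month 3 and Early Discontinuation, with no condition and no footnote.

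**Endpoint and safety sections.** Section 6 says "A total score will be calculated for each subject", and 9.3.6 says "A total score will be generated for each subject". Section 9.3.6 also covers unscheduled visits, but introduces the scale with "In addition, the infection will be assessed on a binary scale", which leans towards the conditional reading.

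**SAP.** Section 13.2.3 has infection diagnosed by CDC criteria, while 13.2.3.1 evaluates incidence through the four signs. Section 13.2.3.2 sums four indicators, each "equal to 0 if the presence of each category is not recorded or is missing", and adds that "the Wound Infection Score will have a maximum value of 4, and a minimum value of 0".

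**The concern.** A site working from Section 8 and a site working from the Schedule would collect different data for the same endpoint. Under Section 8 the signs are noted only after the infection call, so the score becomes an infection indicator multiplied by the number of signs in infected wounds. It would then say almost nothing that the incidence does not already say, and it would inherit any bias in that call. The trial is open-label, and protocol 7.4.7 accepts that its assessments may be biased for that reason.

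The SAP's zero rule hides the gap. A wound whose signs nobody recorded and a wound examined and found free of signs both score 0.

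Section 5 also gives a reason to want the signs in wounds without infection. It lists edema, pain and warmth as foreseeable events with skin adhesives, separately from infection. The protocol's CDC appendix (15.1) adds that redness, warmth and swelling treated as cellulitis do not by themselves meet the physician-diagnosis criterion for superficial infection. A wound can therefore show three of the four scored signs, count as not infected, and go unscored.

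**Working it through.** The plan states no figure on this point, so there is nothing to reproduce. The check sets the texts side by side and then illustrates the size.

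**Step 1: in whom are the signs recorded?**

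| Place | Signs recorded in |
|---|---|
| Protocol 8.2.2, 8.2.3, 8.2.4 | subjects with an infection |
| Protocol 7.1.2 | everyone at the visit (no condition) |
| Protocol 6 and 9.3.6 | everyone, since each subject gets a score |
| SAP 13.2.3.1 | everyone, since incidence is derived from the signs |
| SAP 13.2.3.2 | not stated; unrecorded becomes 0 |

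The Section 8 line cannot be taken fully literally, because incidence cannot be evaluated only in those already infected. The charitable reading applies the condition to the criteria score alone. The score is then still collected only after an infection is found, so the conflict remains.

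**Step 2: illustration of size.**

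Inputs: 189 subjects, 126 and 63 per arm (protocol 10.2); infection 3.6%, edema 9.7%, pain 6.1%, warmth 1.3% (protocol 5, other skin adhesives). Assumptions: these rates apply to both arms here, share a denominator, and describe signs present at the scored visits. Section 5 gives no erythema rate, so erythema is left out.

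- Signs recorded under Section 8: 189 × 0.036 = 6.8 subjects (126 × 0.036 = 4.5; 63 × 0.036 = 2.3).
- Score set to 0 without recorded signs: 189 − 6.8 = about 182 subjects.
- Expected with edema: 189 × 0.097 = 18.3.
- Edema without infection, if every infected subject also has edema: 189 × (0.097 − 0.036) = 189 × 0.061 = 11.5 (126 × 0.061 = 7.7; 63 × 0.061 = 3.8). Under the assumptions this is a minimum.
- Any of edema, pain or warmth without infection, if the three signs never overlap and are independent of infection: 189 × (0.097 + 0.061 + 0.013) × (1 − 0.036) = 189 × 0.171 × 0.964 = 31.2.

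On these assumptions, roughly 12 to 31 subjects could have a sign without infection and be scored 0, against about 7 whose signs are recorded.

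**The case against.** **The endpoint concerns infection.** The objective is to compare infection incidence, the SAP calls the result a Wound Infection Score, and 9.3.6 applies the scale to the infection. No objective promises a comparison of local reactions without infection. This stands as far as it goes: a score meant only for infected wounds would be a legitimate choice. It is not what Section 6, the Schedule or SAP 13.2.3.1 describe, and a summary that fills in 0 for everyone else would not suit it either.

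**Local reactions have other routes.** Adverse events are recorded at every visit and are the main safety endpoint. The mHCS has an inflammation item, subjects rate wound pain at Day 10 and Month 1, and POSAS covers pain and vascularity. A reader might infer that an excess of local reactions would be invisible to the trial; the documents do not support that. These routes are not equivalent, though. Adverse events are elicited by general questions without prompting (9.3.2.1), and none of the other scales asks specifically about edema or local warmth.

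**The score exists for everyone.** A reader might infer that only infected subjects have a score, or that both arms would show nothing but zeros. Neither follows. The SAP gives every subject a value from 0 to 4, and infected wounds can score above 0. What may be lacking is observation of the signs.

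**The counts are soft.** The Section 5 rates carry no time point and may not share a denominator, and edema that has resolved by the visit scores 0 under any rule. The counts show scale and are not a forecast.

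**Conclusion.** The point holds as a conflict between Section 8 and the rest of the plan, made worse by the SAP's zero rule. If sites follow Section 8, the four signs are seen only in wounds already called infected, and the summary cannot separate unassessed from sign-free.

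The eCRF is not among the documents, so they do not show what sites actually record; the finding is that the instructions disagree. The harm is limited to one secondary score that is only described, and the primary non-inferiority test is untouched. Under the assumptions listed with the calculation, signs would be recorded in about 7 of 189 subjects while at least about 11 to 12 had edema without infection. Describing those subjects' reactions as non-infectious is an inference from the separate listing in Section 5, which does not use that term. The change is worth making because it is cheap and settles what is collected.

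**What to change.** 1. In protocol 8.2.2, 8.2.3 and 8.2.4, delete the clause that makes the evaluation conditional on an infection.
2. State that the CDC infection diagnosis (yes/no) and each of the four signs (yes/no) are recorded for every subject seen at Day 10, Month 1, Month 3 and Early Discontinuation, in line with 7.1.2, and at unscheduled visits, in line with 9.3.6. Align the eCRF.
3. In SAP 13.2.3.2, keep a missing sign as missing and reserve 0 for a sign assessed and absent. This also agrees with the SAP's general rule in 16.1.1.7. Without this step, removing the condition is only a partial repair.
4. In SAP 13.2.3.1, report CDC-diagnosed infection separately from the sign score.
5. Present the score for all subjects and for those without a diagnosed infection.

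The cost is four tick boxes at visits already planned, plus wording changes in both documents. Some signs at Day 10 will reflect normal healing, so the score should not be read as a measure of infection on its own; the separate presentation in step 5 helps with that. The change concerns data collection and reporting only.

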### **8.2.3 End-of-treatment Visit (Month 3)**

The following procedures will be performed at the Month 3 visit:

- Record concomitant medication
- Record AEs
- Record of incidents and device performance, device-related complaints
- Evaluation of wound infection, if an infection occurred (incidence and criteria score)
- Patient and Observer Scar Assessment Scale completed by subject and investigator

### **8.2.4 Early Discontinuation Visit**

The following procedures will be performed at the Early Discontinuation Visit:

- Record concomitant medication
- Record AEs
- Record of incidents and device performance, device-related complaints
- Evaluation of wound infection, if an infection occurred (incidence and criteria score)
- Patient and Observer Scar Assessment Scale completed by subject and investigator
- Subject-completed satisfaction questionnaire (completed if Early Discontinuation is before the Month 1 visit or if the questionnaire has not previously been completed)
- Modified Hollander Cosmesis Scale (mHCS) completed by investigator (completed if Early Discontinuation is before the Month 1 visit or if the questionnaire has not previously been completed)
- Subject-related questionnaire completed by investigator (completed if Early Discontinuation is before the Month 1 visit or if the questionnaire has not previously been completed)
- Product-related questionnaire completed by the investigator (completed if Early Discontinuation is before the Month 1 visit or if the questionnaire has not previously been completed)

- 
- Evaluation of dehiscence (completed if Early Discontinuation is before the Month 1 visit)
  - Collection of subject diary (collected if the diary has not previously been collected)

The overall study duration for each subject is up to 4 months.

## 9 EFFICACY, SATISFACTION QUESTIONNAIRES, AND SAFETY

The planned schedule of assessments is in Section 7.1.2.

### 9.1 Efficacy Assessments

- Total dehiscence rate assessed at the Day 1, Day 10, Month 1, and Early Discontinuation (if earlier than Month 1) study visits.
- Classification of dehiscence:
  - Partial dehiscence not requiring re-treatment;
  - Dehiscence to original depth/length not requiring re-treatment (eg, closure with secondary intention);
  - Any dehiscence requiring re-treatment (including draining, debridement, closure, management of infection, etc.).
- Classification of dehiscence according to their grade (World Union of Wound Healing Societies Scale):
  - Dermal layer only
  - Subcutaneous layer exposed, fascia not visible
  - Subcutaneous layer and fascia exposed
  - Any area of fascial dehiscence with organ space, viscera or bone exposed

### 9.2 Satisfaction Questionnaires

- Patient and Observer Scar Assessment Scale (Section 15.3) will be completed by the subject and investigator at the Month 1 and Month 3 visits or the Early Discontinuation visit (Section 7.1.2).
  - The POSAS is a questionnaire that was developed to assess scar quality. It consists of 2 separate 6-item scales (Observer Scale and Patient Scale), both of which are scored on a 10-point rating scale.
  - Each scale has an overall “opinion” with 1 being no pain, no itching, or normal skin and 10 being worst scar imaginable with pain and itching.
- Modified Hollander Cosmesis Scale (Section 15.4) is completed by investigator at the Day 10, Month 1, and Early Discontinuation (if earlier than Month 1 or if the questionnaire has not previously been completed) visits (Section 7.1.2).
  - The mHCS consists of 6 wound characteristics, evaluated as “poor” or “good”

- 
- Each of the characteristics is graded on a 0 (no/good) or 1 (yes/poor) point scale. A total cosmetic score is derived by the addition of the scores.
  - One product-related questionnaire for investigators (Section 15.5) will be completed for each site when the last randomized subject at the site completes the Month 1 visit (Section 7.1.2). This questionnaire will be completed at the Early Discontinuation visit if the visit is earlier than the Month 1 visit or if the questionnaire has not previously been completed.
    - This questionnaire consists of 8 yes/no questions and 1 opinion question that evaluate the investigator's experience with use of the adhesive (ie, instructions easy to understand, preparation of the syringe being easy and fast, glue hardening time).
  - Subject-related questionnaire completed by investigators (Section 15.6) will be done at the Day 0, Month 1, and Early Discontinuation (if earlier than Month 1 or if the questionnaire has not previously been completed) visits and if there is premature removal of the adhesive (Section 7.1.2).
    - This questionnaire consists of 5 yes/no questions that assess the investigator's experience applying the adhesive (ie, easy to use, fast, without complications), a visual analog scale that rates usability of the product from 1 to 100, and 1 question that evaluates satisfaction with the adhesive. The questions are categorized into 3 sections, each section to be completed at different visits.
  - A subject-completed questionnaire (Section 15.7) will be done at the Day 10, Month 1, and Early Discontinuation (if earlier than Month 1 or if the questionnaire has not previously been completed) visits (Section 7.1.2).
    - The questionnaire at the Day 10 visit consists of 5 yes/no questions that evaluate the subject's experience with the adhesive, 1 question that rates the effect of the closed wound on several daily activities (ie showering, getting dressed), 1 question that evaluates satisfaction with the wound closure, and visual analog scales which rate pain on a scale of 1 to 10.
    - The questionnaire at the Month 1 visit consists of 3 questions including a visual analog scale which rates pain on a scale of 1 to 10, and 2 questions relating to the subject's overall satisfaction with the wound closure.

Note: For children, parents or legal guardians may assist in the completion of the questionnaires.

### 9.3 Safety Assessments

- Adverse events.
- Wound infection incidence assessed at the Day 10, Month 1, and Month 3/Early Discontinuation study visits (diagnosed according to the Centers for Disease Control and Prevention [CDC] criteria for surgical site infection).
- Wound infection assessed on a binary scale ("1 - yes" or "0 - no") for the following criteria (total score):

- 
- Presence of erythema
  - Presence of edema
  - Presence of pain at rest
  - Presence of elevated temperature at target wound area

